1.2 OBJECTIVE AND ENDPOINTS

Table 1 - Objectives and endpoints

Objectives	Endpoints
Primary 
To describe the time to tolerization (ITI success, i.e., inhibitor titer <0.6 BU/mL, rFVIIIFc incremental recovery [IR] $\geq 66\%$ of the expected IR, and $t_{1/2} \geq 7$ hours) with rFVIIIFc in patients within a maximum of 12 months (48 weeks) of ITI treatment.	
Time to tolerization with a maximum of 12 months (48 weeks) of ITI treatment offered in the study (tolerization defined as inhibitor titer <0.6 BU/mL, rFVIIIFc incremental recovery [IR] of $\geq 66\%$ of expected, and half-life [$t_{1/2}$] of ≥ 7 hours).

Objectives	Endpoints
Secondary 
• To describe the outcome of ITI treatment• To describe the relapse rate over the 48-week (12-month) period following successful ITI performed with rFVIIIFc• To describe the intercurrent bleeding during the ITI Period and during the 48-week (12-month) period after successful ITI performed with rFVIIIFc• To describe the safety and tolerability of rFVIIIFc when used for ITI• To evaluate the impact of ITI treatment with rFVIIIFc on health economics and adherence	
• ITI success:
- Confirmed negative titers consisting of 2 consecutive negative inhibitor assessments within 2 weeks (± 3 days) based on local laboratory results <0.6 BU/mL by the Nijmegen-modified Bethesda assay; determination of negative titer based on the Bethesda assay is acceptable at sites that have not yet adopted the Nijmegen-modified Bethesda assay.- IR ≥ 1.32 IU/dL per IU/kg in 2 consecutive assessments representing $\geq 66\%$ of the expected IR 2 IU/dL per IU/kg.- $t_{1/2} \geq 7$ hours.• Occurrence of relapse (defined as confirmed positive inhibitor titer ≥ 0.6 BU/mL, abnormal recovery after tolerance is achieved, and $t_{1/2} < 7$ hours) during the Tapering or Follow-Up Periods• Number of bleeding episodes during the ITI Period and during the 48-week (12-month) period after successful ITI performed with rFVIIIFc• Adverse events and serious adverse events• Number of days away from work or school• Number of hospitalization days• Adherence (defined as percentage of administered doses versus planned doses)• Consumption of rFVIIIFc (measured in total rFVIIIFc use)
Tertiary/exploratory 	

Objectives	Endpoints

1.2.1 Estimands

Not applicable.

2 SAMPLE SIZE DETERMINATION

Because the number of patients who have severe hemophilia A and have developed inhibitors is small, the determination of sample size for this study is constrained by the availability of patients. To describe the duration of time needed to develop tolerization from the onset of ITI, the study plans to prospectively enroll up to 30 patients who are to receive ITI for the first time.

3 ANALYSIS POPULATIONS

For the purpose of statistical analyses, 3 analysis sets are defined based on the following criteria:

Table 2 - Populations for analyses

Population	Description
ITI full analysis set (ITIFAS)	This set will include all patients who received at least 1 infusion of rFVIIIFc. All analyses describing efficacy and safety during the ITI treatment period will be based on this analysis set. This analysis set will also be used for analysis of endpoints which summarize cumulative results from ITI, tapering, and follow-up periods.
Tapering period full analysis set (TPFAS)	This set will include all patients who entered the tapering period of the study. All analyses describing efficacy and safety during this study phase will be based on this analysis set. This analysis set will also be used for analysis of endpoints which summarize cumulative results from tapering and follow-up periods.
Follow-up period full analysis set (FUPFAS)	This set will include all patients who entered the follow-up period of the study. All analyses describing efficacy and safety during this study phase will be based on this analysis set.

4 STATISTICAL ANALYSES

4.1 GENERAL CONSIDERATIONS

Continuous data will be summarized using the number of observations available, mean, standard deviation (SD), median, minimum, and maximum. The 25th (Q1) and 75th (Q3) percentiles and 95% confidence intervals may be presented where appropriate. Categorical and ordinal data will be summarized using the count and percentage of patients.

In general, event time variables will be summarized in two ways. For the subset of patients who experience the event of interest, the data will be summarized using standard descriptive statistics for continuous variables as described above. In addition, Kaplan-Meier estimates will be provided for ITI full analysis set regardless whether a patient experiences the event of interest. Patients who do not reach an event will be censored on the date of the last on-study follow-up visit unless otherwise specified in the SAP.

The baseline value is defined as the last available value before the first dose of ITI with rFVIIIFc.

Unless otherwise specified, analyses will be performed for all treated patients.

Observation period

The observation period will be divided into 3 segments:

- **ITI period** starts on the day of the first dose of ITI with rFVIIIFc. For those who successfully tolerized and entered the tapering period, the end of the ITI period is the day before the first visit of the tapering period. For those who did not successfully tolerate per protocol, the end of the ITI period is the day of the last study visit.
- **Tapering period** starts on the day of first visit of the tapering period and ends on the day of the last visit of the tapering period. For those who did not enter the follow-up period, the tapering period ends on the day of the last study visit.
- **Follow-up period** starts on the day after the last visit of the tapering period and ends on the day of the last study visit.

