**Table 2: Schedule of Activities for the Tapering and Follow-Up Periods After Successful Tolerization**

Activities	Tapering Period 	Follow-Up Period 	EOT 	
	Tapering Initiation Visit/Telephone Call,  Week 2, 4, 8, 12, and 16 Visits	Week 28 and 40 Visits 	EOT Visit	Final Safety Follow-Up
	Starting at ITI success and continuing for a minimum of 16 weeks with visits after 2 weeks ( $\pm 3$ days), 4 weeks ( $\pm 1$ week), and then every 4 th week ( $\pm 1$ week)	Week 28 and 40 visits ( $\pm 2$ weeks)  following ITI success	Week 48 visit ( $\pm 2$ weeks) following ITI success OR upon relapse	7 to 14 days after EOT Visit
Physical Examination	X	X	X	
Height (cm)			X	
Weight (kg)	X	X	X	
Vital Signs 	X	X	X	
Hematology (Local Laboratory) 	X		X	
Blood Chemistry (Local Laboratory) 	X		X	
Urinalysis (Local Laboratory) 	X		X	
Nijmegen-Modified Bethesda Inhibitor Assay (Both Local and Central Laboratories) 	X	X	X	
Anti-rFVIIIFc Antibody (ADA) (Central Laboratory)	X	X	X	

CONFIDENTIAL

The information contained herein may not be used, disclosed, or published without the written consent of Bioverativ Therapeutics Inc.

Activities	Tapering Period 	Follow-Up Period 	EOT 	
	Tapering Initiation Visit/Telephone Call,  Week 2, 4, 8, 12, and 16 Visits	Week 28 and 40 Visits 	EOT Visit	Final Safety Follow-Up
	Starting at ITI success and continuing for a minimum of 16 weeks with visits after 2 weeks ( $\pm 3$ days), 4 weeks ( $\pm 1$ week), and then every 4 th week ( $\pm 1$ week)	Week 28 and 40 visits ( $\pm 2$ weeks)  following ITI success	Week 48 visit ( $\pm 2$ weeks) following ITI success OR upon relapse	7 to 14 days after EOT Visit
Blood Sample for Immune Cell Characterization (Required) (Central Laboratory) 	X		X	
rFVIIIFc Dosing 	X	X	X	
FVIII Activity for IR (Both Local and Central Laboratories) 	X	X		
FVIII Activity for $t_{1/2}$ Evaluation (Both Local and Central Laboratories) 			X	
FVIII Activity Level (Both Local and Central Laboratories) 		X	X	
EPD Review, Including Review of Bleeding Episodes and rFVIIIFc Dosing Accountability 	X	X	X	
Nonserious Adverse Events	X	X	X	X
Serious Adverse Events	X	X	X	X

CONFIDENTIAL

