## 7.2.2. Immune Tolerance Induction Period

The first dose of rFVIIIFc ITI will be administered at the Baseline Visit, and treatment will continue until ITI success is declared or for a maximum of 48 weeks (12 months). The ITI regimen consists of rFVIIIFc 200 IU/kg/day ( $\pm$ 8 hours), which may be given as once-daily injections or divided into several injections per day at the discretion of the Investigator.

Subjects will visit the clinic 2 and 4 weeks after enrollment and then every fourth week until 48 weeks (12 months) or until a negative inhibitor ( $<0.6$  BU/mL) has been obtained. After the negative inhibitor results, visits will be scheduled every other week until ITI success or failure is declared.

The Investigator's assessment of ITI outcome will be based on results from the local laboratory. If the local laboratory results are inconclusive, the Investigator may use the central laboratory results to determine ITI outcome. During the ITI Period, subjects will undergo procedures and assessments at designated visits per [Table 1](#). Samples for inhibitor testing and assessment of FVIII activity levels will be analyzed at the local laboratory and at the central laboratory. Investigator treatment and assessment of inhibitor status will be based on results from the local laboratory. Negative inhibitor testing results must be confirmed (i.e., 2 consistent results at 2 consecutive assessments). See Section [7.2.2.2](#) for specific definitions of ITI outcomes.

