### **7.2.3. Downtitration (Dose Adjustment) Between ITI Treatment and the Tapering Period**

If FVIII activity levels rise above 200 IU/dL, after the inhibitors are negative but before all of the ITI success criteria are met, the dose will be adjusted according to Investigator judgment to maintain the FVIII activity levels between 100 and 200 IU/dL. This dose adjustment will not be considered part of the Tapering Period, and the subject will maintain the schedule of assessments per the ITI Period.

Once  $t_{1/2}$  has been determined to be  $\geq 7$  hours, the Investigator may have a Tapering Initiation Visit and/or a Tapering Initiation Telephone Call. If the subject has already begun downtitration from the 200 IU/kg/day ITI dose, the subject will return for the next scheduled visit (the Tapering Initiation Visit) 2 weeks from the visit at which  $t_{1/2}$  was determined to be  $\geq 7$  hours. If the subject has not already downtitrated when  $t_{1/2}$  is determined to be  $\geq 7$  hours, the Investigator can make a telephone call to instruct the subject to begin downtitrating immediately (Tapering Initiation Telephone Call). Subject's subsequent visit, which will occur 2 weeks from the visit at which  $t_{1/2}$  was determined to be  $\geq 7$  hours, will be the Tapering Initiation Visit.

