### **7.2.4. Tapering Period**

Subjects who have met the criteria for ITI success will enter the Tapering Period. Further details about the recommended dosing regimen for tapering are described in Section 11. Subjects with bleeding episodes during the Tapering Period will be tested for recurrence of inhibitors and monitored for relapse.

During the Tapering Period, treatment with bypassing agents may be considered if bleeding is unresponsive to treatment with rFVIIIFc (see Section 7.2.2.1). Testing for recurrence of inhibitors will be performed throughout the Tapering and Follow-Up Periods.

Subjects will visit the clinic 2 and 4 weeks after the first visit in the Tapering Period and then every fourth week for a minimum of 16 weeks (4 months). The duration of the Tapering Period may be modified by the Investigator with the Sponsor Medical Monitor's approval based on the subject's clinical response. If the Tapering Period exceeds 16 weeks (4 months), unscheduled visits will be performed every 4 weeks (1 month) or per the Investigator's judgment.

During the Tapering Period, subjects will undergo procedures and assessments at designated visits per the schedule of events (see Table 2). At each visit, samples for inhibitor titer and IR assessments will be drawn and sent to the local and central laboratories to monitor for relapse.

If the subject experiences bleeding during the Tapering Period, the treatment of the bleeding will be left to the discretion of the Investigator. During the Tapering Period, treatment with bypassing agents may be considered if bleeding is unresponsive to treatment with rFVIIIFc (see Section 7.2.2.1).

Throughout the Tapering Period, rFVIIIFc administration, bypassing agent administration, and any bleeding episodes will be collected by the subject and/or his caregiver in the EPD. The EPD data will be reviewed by the Investigator on an ongoing basis and discussed with the subject at each visit.

CONFIDENTIAL

The information contained herein may not be used, disclosed, or published without the written consent of Bioverativ Therapeutics Inc.

Page 44

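### The SAP starts Tapering at the first tapering visit and the protocol at ITI success, so about 14 post-success days per tolerized patient are counted as ITI

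*SAP*

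**What the plan says.** SAP 4.1 divides observation into three segments. For patients who were tolerized and entered tapering, "the end of the ITI period is the day before the first visit of the tapering period". The second segment, for tapering, "starts on the day of first visit of the tapering period and ends on the day of the last visit of the tapering period". The SAP does not define which contact counts as the first tapering visit and does not mention a telephone call.

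The protocol ties the change of period to success:

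- Table 2 heads the Tapering column "Starting at ITI success and continuing for a minimum of 16 weeks with visits after 2 weeks". It counts the Week 28, 40 and 48 visits from ITI success.
- Section 7.2.4: "Subjects who have met the criteria for ITI success will enter the Tapering Period".
- Section 7.2.3, for a patient whose dose was already reduced: "the subject will return for the next scheduled visit (the Tapering Initiation Visit) 2 weeks from the visit at which" half-life was found to be at least 7 hours. For a patient whose dose was not yet reduced, "the Investigator can make a telephone call to instruct the subject to begin downtitrating immediately", and the Tapering Initiation Visit follows at the same two-week point ("which will occur 2 weeks from the visit at which" the half-life criterion was met).

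The SAP reports bleeding (4.4.1), exposure, consumption, adherence and tapering doses (4.7.1) and adverse events (4.7.2) by these segments. One secondary endpoint (SAP Table 1) is the number of bleeding episodes in the ITI Period and in the 48 weeks after successful ITI.

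**The concern.** Under the SAP rule a patient who has met all three success criteria stays in the ITI period until the next clinic visit. Those days can include the start of the dose reduction. They are added to ITI and removed from Tapering, together with any bleeds, adverse events and doses that fall in them.

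Three results are exposed most directly:

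- The post-success bleeding summary omits roughly the first two of the 48 weeks that the endpoint names.
- The reported first dose in the Tapering period may miss the dose that was started by telephone.
- The 90-day minimum for the ITI bleeding rate can be met with days that follow success.

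The relative effect is largest in the patients who tolerize fastest. With up to 17 subjects in the protocol, a few such patients can be visible in the summaries.

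**Working it through.** **Inputs.** Tapering lasts at least 16 weeks and Follow-Up 32 weeks (Protocol 7.2). The end-of-treatment visit is Week 48 ± 2 weeks after ITI success (Table 2). The Tapering Initiation Visit is 2 weeks after the qualifying half-life visit (7.2.3). The 90-day minimum is in SAP 4.4.1.1. The annualized bleeding rate is bleeds / (days / 365.25) (SAP 4.4.1.1).

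**1. The protocol's own clock.** If Tapering starts at success, 16 + 32 = 48 weeks, which reproduces the Week 48 visit. If it starts at a visit two weeks later, 2 + 16 + 32 = 50 weeks, which fits only at the edge of the ± 2 week window. The visit schedule was therefore built from ITI success.

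**2. Length of the gap.** Let the qualifying half-life visit be day D. Under Table 2, Tapering runs from D. If the Tapering Initiation Visit is the first tapering visit, it falls on D + 14 and the SAP's ITI period runs through D + 13. Days D to D + 13 are 14 days, or 11 to 17 if a ± 3 day visit window is assumed.

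**3. Shares.** With success at Week w, the ITI time before success is 7w days and the SAP's ITI period is 7w + 14 days.

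| Quantity | Calculation | Result |
|---|---|---|
| Share of SAP ITI period, Week 17 | 14 / 133 | 10.5% |
| Share of SAP ITI period, Week 28 | 14 / 210 | 6.7% |
| Relative to minimum Tapering Period | 14 / 112 | 12.5% (11 to 17 days: 9.8% to 15.2%) |
| Relative to 48 weeks after success | 14 / 336 | 4.2% (3.3% to 5.1%) |

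**4. Bleeding rate.** If no bleed falls in the gap, the ITI rate drops by the share above, 10.5% for success at Week 17. A bleed in the gap moves the rates the other way. As an illustration with assumed counts, take success at Week 17, 2 bleeds before success, and 2 bleeds in the 336 days after it, one of them in the gap:

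- ITI rate: 2 / (119 / 365.25) = 6.1 per year becomes 3 / (133 / 365.25) = 8.2.
- Post-ITI rate: 2 / (336 / 365.25) = 2.2 per year becomes 1 / (322 / 365.25) = 1.1.

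**5. The 90-day minimum.** This is read as observation within the ITI period. A patient passes only because of the added days when the time to success is below 90 days and that time plus 14 is at least 90, so at about 76 to 89 days.

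**6. Consumption.** The documents leave the dose in these days to the investigator, so any size is conditional. If 200 IU/kg/day were halved for all 14 days, mean daily ITI consumption would change by (119 × 200 + 14 × 100) / 133 / 200 − 1 = −5.3% at Week 17. At Week 28 it would change by (196 × 200 + 14 × 100) / 210 / 200 − 1 = −3.3%.

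**The case against.** The strongest reply is that the protocol is not uniform, so the SAP picked one of two anchors and did not contradict a clear rule. The title of Section 7.2.3 places downtitration between ITI treatment and Tapering. Section 7.2.4 counts tapering visits from the first visit in that period, while Table 2 counts from ITI success. Table 2 also lists the initiation visit and the telephone call as one contact, so the SAP might treat a recorded call as the first visit. The call is optional. This stands, and it is why the finding depends on reading the clinic visit as the first tapering visit. It does not remove the mismatch. The protocol's statement that a dose adjustment is not part of Tapering covers only adjustment before all success criteria are met, and the 48-week clock works only from success.

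Several stronger readings are tempting and are not supported:

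- *That all by-period results are biased.* Adherence compares administered with prescribed amounts, so a prescribed reduction changes both terms and creates no mechanical bias.
- *That early responders show a 20% effect on annualized rates.* Success at Week 8 gives 14 / 70 = 20% of the days, but a 70-day ITI period fails the 90-day minimum that the SAP sets for the ITI bleeding rate and for annualized consumption.
- *That annualized consumption is understated by a known amount.* Half-life sampling can last 48 hours and the result must be available before a call. Some patients were already on a reduced dose. If the SAP's study-length denominator means the whole study, the ITI boundary does not enter at all.
- *That a 50-week ITI period after success at Week 48 breaks the 48-week maximum.* That maximum limits ITI treatment, whereas SAP 4.1 defines observation segments. Table 1, footnote 1 already allows confirmatory testing after Week 48.

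**Conclusion.** The concern holds in a limited form. With the Tapering Initiation Visit taken as the first tapering visit, SAP 4.1 counts about 14 post-success days per tolerized patient as ITI. The size in days is firm to within the visit window. The effect on any rate depends on when success occurs and on what happens in those days.

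It touches by-period bleeding rates, exposure, consumption, adverse event allocation, the reported first tapering dose, and who qualifies for the ITI bleeding rate. Adverse events and consumption are also summarized over all periods combined, and those totals do not change.

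A reader might infer that the primary result is at risk. It is not. Time to tolerization, ITI outcome and time to relapse rest on the dates when criteria were met, not on this boundary. No hypothesis test is planned, so the issue is correct description of small-sample summaries. The change is worth making before the final analysis.

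**What to change.** In SAP 4.1, define the boundary by the ITI success date and state that this is the visit date of the qualifying half-life assessment recorded in the eCRF. SAP 4.3.1 already says that the investigator records the date on which the half-life criterion is met. End the ITI period on that date and start Tapering the next day, whether the next contact is a visit or a call. Post-success summaries then cover the 48 weeks after ITI success. Because the success day itself stays in ITI, 13 of the nominal 14 days move.

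Reconcile Protocol Table 2, 7.2.3 and 7.2.4 with SAP 4.1, so that one anchor governs the tapering visits and the analysis periods. If the sponsor prefers the visit anchor, the SAP should define the first tapering visit, state the departure from Table 2, and add a sensitivity summary by success date.

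The cost is one SAP sentence and one derived date, with no new data. There is a small downside: a few days at the ITI dose, before tapering actually begins, may be counted as Tapering. No dose or clinical rule is proposed.

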4.2 PARTICIPANT DISPOSITIONS

Patient disposition will be summarized for all enrolled in the study. The number (%) of patients included in each of the analysis populations (ITIFAS, TPFAS, and FUPFAS) listed in [Table 2](#) will be summarized.

The number (%) of patients in the following categories will be provided (overall and by study period):

- Enrolled patients
- Participants who completed the study period as per protocol

- Participants who did not complete the study period as per protocol and main reason for study discontinuation

In addition, the number (%) of patients enrolled will be summarized by geographical region, country and site. The number (%) of patients attending key study visits will be summarized by visit for ITIFAS.

A listing including the duration in the study, date of the last visit/period, and the reason for early termination/withdrawal for patients who did not complete the study will be provided.

Protocol deviations

Protocol deviations will be recorded, monitored throughout the study and finalized at the end. Major and minor protocol deviations/violations are to be pre-specified prior to database lock. There is no plan of excluding patients from statistical analyses as the result of protocol deviation. Critical and major protocol deviations (programmatic or manual) will be summarized in the enrolled population.

4.3 PRIMARY ENDPOINT(S) ANALYSIS

4.3.1 Definition of endpoint(s)

The primary endpoint of this study is time to tolerization with a maximum of 48 weeks (12 months) of ITI treatment offered in the study (tolerization defined as inhibitor titer <0.6 BU/mL, rFVIIIFc incremental recovery [IR] $\geq 66\%$ of the expected IR, and $t_{1/2} \geq 7$ hours).

Negative inhibitor

Inhibitor titer value <0.6 BU are considered negative. To confirm that a patient's inhibitor titer has reached negativity, a consecutive second sample with a titer value <0.6 BU at the next visit is required.

Results from local lab will be used for this determination. If the local lab results are not available, the results from the central lab will be used. Occurrence and date of negative titer associated with ITI success will be recorded in the eCRFs by the investigator.

Normal incremental recovery (IR)

IR ≥ 1.32 IU/dL per IU/kg ($\geq 66\%$ of the expected IR 2 IU/dL per IU/kg) is considered normal IR. To confirm the occurrence of normal IR, a consecutive visit with a normal IR is required.

Results from local lab will be used for this determination. If the local lab results are not available, the results from the central lab will be used. Occurrence and date of normal IR will be recorded in the eCRFs by the investigator.

Half life ≥ 7 Hours

Achieving $t_{1/2} \geq 7$ hours is the final PK goal of the ITI treatment. Results from local lab will be used for this determination. If the local lab results are not available, the results from the central lab will be used.

Occurrence and date of $t_{1/2} \geq 7$ hours will be recorded in the eCRFs by the investigator.

